6.4 MEASURES TO MINIMIZE BIAS: RANDOMIZATION AND BLINDING

We will use stratified permuted block randomization with random block sizes to allocate patients in a 1:1 allocation to the 14 or 28 tube sizes. The randomization lists will be generated by a study statistician using SAS Enterprise Guide version 6.1 and stratified by location (Emergency Department and Surgical & Trauma ICU). Randomization lists will be provided to the study coordinator and another study team member not affiliated with clinical care and assessments to place the allocations into number opaque envelopes. These envelopes will be pulled sequentially by the surgeon or study team as a patient is deemed provisionally eligible for the study preserving allocation concealment. The ID of the envelope is recorded in the patient's research record.

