Outcome measures	
Aim I
 
Primary outcome:
 
 • Retained hemothorax requiring an additional intervention, either video-assisted thoracoscopic surgery (VATS) or additional thoracostomy tube placement. 
Secondary outcome:
 
 • Duration of chest tube placement [Time Frame: 90 days] • Length of hospitalization • Subjective pain [Time Frame: 5 minutes pre- and post-insertion], Assessed with 0-10 numeric pain rating scale • Hemodynamic stability post-insertion (determined by vital signs: temperature, heart rate, blood pressure, oxygen saturation) • Initial drainage from chest tube at 5 minutes [Time Frame: 5 minutes] • Tube specific complications: Air leak, tube malposition, & tube migration [Time Frame: 90 days] • Time to radiographic resolution of pneumothorax/hemothorax/hemopneumothorax [Time Frame: 90 days] • Recurrent pneumothorax/hemothorax/hemopneumothorax after tube removal • Readmission for chest tube related complications [Time Frame: 90 days] 
Aim II
 
 • Empyema rates in traumatic pneumothorax, hemothorax, and hemopneumothorax
Description of Study Intervention:	Placement of 14 Fr Thal tube or 28 Fr Chest Tube for Hemopneumothorax.
Study Duration:	2 Years
Randomization	Permuted block randomization with random block sizes to allocate patients in a 1:1 allocation to the 14 or 28 tube sizes. The randomization lists will be generated using SAS Enterprise Guide version 6.1. All study staff collecting and recording data for the trial will be masked to the tube size that was used during the procedure.

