5 STUDY POPULATION

5.1 INCLUSION CRITERIA

- The patient is admitted to the trauma service.
- The patient has a hemothorax and/or or hemopneumothorax, requiring thoracostomy tube placement.
- Thoracostomy tube placement is able to be performed or witnessed by an investigator listed on the study.
- The patient has not had a chest tube in the past year.
- The patient is ≥ 18 years of age.
- In the event the patient is decisionally impaired, consent will be obtained from the individual's legally authorized representative (LAR) or from the individual's healthcare power of attorney (HPA).
- In the instance of reversible impairment, initial consent would be obtained from the LAR/HPA and the patient will be approached for consent once he/she is deemed mentally competent by the care provider.

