5.4 STRATEGIES FOR RECRUITMENT AND RETENTION

Subject enrollment will take place at a single American College of Surgeons designated Level I trauma center. A partial waiver of authorization will be requested for the purposes of pre-screening for enrollment via electronic medical record review. All patients 18 years of age and older sustaining trauma that requires therapeutic tube thoracostomy will be screened for study eligibility by the research staff. Participants will be approached for consent as soon as it has been determined that the patient has met all inclusion criteria and no exclusion criteria.

The study design aims to maintain high patient retention throughout the study period. Subject retention strategies include limiting study involvement to three months and limiting subject follow-up to electronic medical record review supplemented by a single telephone call.

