9.4 STATISTICAL ANALYSES

9.4.1 GENERAL APPROACH

All analyses for this randomized trial will follow the intention to treat principle with an additional per protocol analysis given the non-inferiority hypothesis. We will first compare the baseline characteristics of the patients by group to assess for statistically significant or clinically meaningful imbalances. If either exists, these factors will be taken into account in sensitivity analyses for the primary and secondary outcomes.

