9.4.2 ANALYSIS OF THE PRIMARY EFFICACY ENDPOINT(S)

The rates of failure of drainage (primary outcome) will be estimated as proportions and compared between the two groups using a Chi-square test corrected for the non-inferiority hypothesis. We will present the findings using the difference in the proportions (rate in small group –rate in large group) and corresponding 95% upper confidence limit.

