10 SUPPORTING DOCUMENTATION AND OPERATIONAL CONSIDERATIONS

10.1 REGULATORY, ETHICAL, AND STUDY OVERSIGHT CONSIDERATIONS

10.1.1 INFORMED CONSENT PROCESS

The IRB approved informed consent form (ICF) will adhere to ICH GCP guidelines and comply with the United States Code of Federal Regulations as detailed in 21 CFR §50.25 and the Declaration of Helsinki.

Once eligibility has been confirmed, an investigator/research coordinator will approach each patient or legally authorized representative (LAR) to explain the nature of the study, its purpose, expected duration, alternative forms of therapy available, benefits and risks of study participation. Patients who are GCS = 15 will be approached prior to thoracostomy tube insertion for study consent. Patients with GCS <15 will either be consented by LAR or approached for self-consent if mentation normalizes within 24 hours of tube insertion. Where consent has been obtained from a LAR; the patient will be approached for consent if the investigator later deems the patient GCS = 15 during the study period.

It is expected that most patients/ LARs will be approached in either the emergency room or intensive care unit for consent. After this explanation and before enrollment, the patient or authorized legal representative will be given ample time and opportunity to read the consent form. Patients/LARs who choose to participate will voluntarily sign and date the form in the presence of the investigator/research coordinator.

It will be pointed out to the patient/LAR that they can refuse to participate in the study or withdraw from the study at any time without prejudice to further care and treatment.

The patient/LAR will be given a copy of the signed and dated informed consent form. The acquisition of informed consent will be documented in the patient's medical records.

Patients/LARs will be informed of any significant new finding which arises during the course of study participation that may affect their decision to continue participation.

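### Randomisation is stratified by location, but the primary comparison and every other planned analysis ignore the strata, at a modest cost in precision

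*Combined protocol and SAP*

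**What the plan says.** Section 6.4 specifies permuted blocks of random size, 1:1, with lists "stratified by location (Emergency Department and Surgical & Trauma ICU"). No third location is named. The envelope ID is kept in the research record. The Randomization entry of the synopsis (1.1) reads "Permuted block randomization with random block sizes to allocate patients in a 1:1 allocation to the 14 or 28 tube sizes" and does not mention strata.

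In 9.4.2 the primary failure rates are "compared between the two groups using a Chi-square test corrected for the non-inferiority hypothesis", and the result is reported as a difference in proportions with a 95% upper limit. The interim test (9.4.4) and the secondary analyses (9.4.3) have no location term either; length of stay, for example, is modelled on group alone. Section 9.4.1 allows adjustment only for baseline factors found to be imbalanced: "these factors will be taken into account in sensitivity analyses for the primary and secondary outcomes". Location is not among the baseline items listed in 6.2.

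On coverage, 5.1 requires that "The patient is admitted to the trauma service" and sets no limit by unit, and 5.4 screens adults "sustaining trauma that requires therapeutic tube thoracostomy will be screened for study eligibility by the research staff". Section 10.1.1 says: "It is expected that most patients/ LARs will be approached in either the emergency room or intensive care unit for consent".

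**The concern.** A factor chosen for stratification is normally one thought to be related to outcome. If it is, the arms are balanced on it by design, so the difference in failure rates varies less than an unstratified standard error assumes. The unstratified upper limit is then a little too high, and in a non-inferiority trial that limit is what is compared with the 8-point margin. The loss is avoidable, because the information needed to remove it is created at randomisation.

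The imbalance rule in 9.4.1 does not repair this. Stratified blocks are meant to prevent imbalance in location, so the rule would rarely bring location in, and then only as a sensitivity analysis. An analysis that follows the randomisation has to be specified in advance.

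A smaller point concerns carrying out 6.4 as written: it does not say which list is used if the envelope is opened somewhere other than the two named units.

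**Working it through.** **Inputs from the plan.** 28 Fr failure rate 7%, 126 per group, 80% power, α = 0.05 (9.2); margin 8 points (8.1); 95% upper limit (9.4.2). The sidedness of α is not stated.

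**Inputs assumed.** The plan gives neither the split of patients between the two locations nor the failure rate in each. All stratum figures below are assumptions.

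**Step 1: reproduce the plan's sample size.** With a true difference of zero, unpooled variance and one-sided 0.05:

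n = (z₀.₉₅ + z₀.₈₀)² × 2p(1−p) / margin² = (1.645 + 0.842)² × 2(0.07)(0.93) / 0.08² = 6.183 × 0.1302 / 0.0064 = 125.8, so 126 per group, as stated. Power at 126 is 80.1%. One-sided 0.025 would give 160. The stated N is therefore that of an unstratified comparison at one-sided 0.05.

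**Step 2: variance within strata against pooled variance.** With a share w of patients in the Emergency Department and failure rates pE and pI:

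ratio = [w·pE(1−pE) + (1−w)·pI(1−pI)] / [p(1−p)], where p = w·pE + (1−w)·pI.

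- 4% v 12%, w = 0.60: p = 0.072; ratio = (0.02304 + 0.04224) / 0.066816 = 0.977. Variance is 2.3% lower and the standard error 1.2% lower.
- 3% v 20%, w = 0.75: p = 0.0725; ratio = (0.021825 + 0.040) / 0.067244 = 0.919. Variance is 8.1% lower and the standard error 4.1% lower.

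**Step 3: effect on the upper limit.** The unstratified half-width is 1.645 × √(2p(1−p)/126).

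- First case: 5.36 points, falling to 5.29, a change of 0.06.
- Second case: 5.37 points, falling to 5.15, a change of 0.22.

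Both are small beside an 8-point margin.

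**Step 4: power and one-sided error, overall rate 7%, 126 per group.** Let SE_t be the pooled and SE_w the within-stratum standard error.

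- Power ignoring strata = Φ[(0.08 − 1.645·SE_t)/SE_w]
- Power using strata = Φ[0.08/SE_w − 1.645]
- One-sided error ignoring strata = 1 − Φ[1.645·SE_t/SE_w]

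| Larger stratum | Rates | Power ignoring strata | Power using strata | Error ignoring strata |
|---|---|---|---|---|
| any | 7% v 7% | 80.1% | 80.1% | 0.050 |
| 70% | 5.5% v 10.5% | 80.2% | 80.3% | 0.049 |
| 70% | 4% v 14% | 80.4% | 81.2% | 0.047 |
| 80% | 5% v 15% | 80.4% | 80.9% | 0.048 |
| 50% | 2% v 12% | 80.5% | 81.4% | 0.047 |

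For gaps up to 10 points the gain is at most 0.9 points of power, and the N for 80% power with a stratified analysis is about 121 to 126 per group. A wider gap gains more: 1.3 points for 1% v 13% in equal strata (80.7% to 82.0%), and about 1.9 points for the 3% v 20% case of Step 2 (79.9% to 81.8%).

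**Step 5: simulation check.** In 200,000 simulated trials per scenario with a Wald limit, unstratified v stratified:

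| Rates (larger stratum) | Power | One-sided error |
|---|---|---|
| 7% v 7% (70%) | 80.3 v 80.6% | 0.056 v 0.056 |
| 5.5% v 10.5% (70%) | 80.6 v 80.9% | 0.056 v 0.057 |
| 4% v 14% (70%) | 80.9 v 81.7% | 0.054 v 0.057 |
| 2% v 12% (50%) | 80.8 v 81.7% | 0.054 v 0.057 |

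The excess over 0.05 comes from the Wald limit and appears in both analyses. The unstratified error is never above the stratified one.

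**The case against.** The strongest reply is that the unadjusted risk difference is a recognised choice, that 126 per group was computed for it, and that the gain is about 1 point of power at most unless the strata differ by more than 10 points. Ignoring the strata errs on the cautious side, so it does not make a false claim of non-inferiority more likely. All of that stands, and it is why this is a point about precision and not about validity. The gain is also not entirely free: with a Wald limit the stratified analysis ran at 0.057 against 0.054 in two of the simulated scenarios, so the method for the limit should be chosen with care.

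Three stronger readings are tempting, and the documents do not support them.

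- *The stratification is wasted.* It is not. The blocks balance the arms by location whatever the analysis; only the use of that balance in the standard error is lost.
- *Some eligible patients have no list and will be lost or misplaced.* The documents are silent on other locations; they do not say that such patients exist or cannot be randomised. The sentence in 10.1.1 concerns where consent is sought, which for patients with GCS below 15 may be up to 24 hours after insertion. It also covers all prospective subjects, including those with pneumothorax alone, who are not randomised. The number randomised outside the two units is unknown and may be zero. A patient drawn from either list is still allocated 1:1. Nothing in the plan says that such patients would drain differently.
- *The synopsis contradicts 6.4.* The synopsis omits the stratification; it does not deny it.

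**Conclusion.** The point holds as one of modest efficiency. The plan stratifies by location and then analyses as if it had not. The cost is roughly 2% to 8% of variance under the two assumed pairs of stratum rates (0.06 to 0.22 points on the upper limit), and at most about 1 point of power when the stratum rates lie within 10 points of each other. If location is unrelated to failure, the cost is nil. These sizes rest entirely on assumed stratum shares and rates. The direction does not: the unstratified standard error is, in expectation, no smaller than the stratified one when the arms are balanced within strata. Neither the validity of the trial nor its sample size is in question. The unstated list for other locations and the silence of the synopsis are matters of missing detail only.

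**What to change.** In 9.4.2, estimate the risk difference (14 Fr minus 28 Fr) and its 95% upper limit stratified by randomisation location with Mantel-Haenszel weights, name the method for the limit, and report the unstratified result as a sensitivity analysis. Take the stratum from the envelope series. Section 6.4 already records the envelope ID; it should add that the numbering identifies the series.

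As clarifications, 6.4 should say which list serves a patient randomised outside the Emergency Department and the Surgical & Trauma ICU, or state that randomisation takes place only there, and should say when location is determined. The synopsis should mention the stratification.

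The cost is wording in 1.1, 6.4 and 9.4.2 and a few lines of analysis code. It needs no extra patients, and N stays at 126 per group. If other locations are added to one of the two lists, that stratum becomes more mixed, which slightly reduces an already small gain.

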6 STUDY INTERVENTION

6.1 STUDY INTERVENTION(S) ADMINISTRATION

Screened subjects eligible for study participation will have their inclusion/exclusion criteria verified by an investigator. The subject will be approached for consent by the research staff and enrolled. Subjects with suspected pneumothorax alone will receive either a small bore (14 Fr) or large bore (28 Fr) tube chosen based on physician preference. Subjects with suspected hemothorax or hemopneumothorax will be randomized to receive either a small or large bore chest tube.

Enrolled subjects will have their thoracostomy tube placement procedure observed and verified by an investigator listed on this protocol. The training level of the individual performing the procedure will be recorded. Maximum barrier precautions for this study will be used during the placement procedure for all prospective subjects. Maximum barrier precautions for this study will be defined as the correct use of proper hand hygiene, a cap, surgical gown, sterile gloves, mask, and a thyroid drape. The institutional standard of care thoracostomy tube Practice Guidelines will be followed.

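### Section 6.4 gives the randomisation lists to the study coordinator and does not separate list holders from consent, enrolment or envelope pulling, so concealment is not secured as claimed

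*Combined protocol and SAP*

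**What the plan says.** Under section 6.4 a study statistician generates 1:1 lists in permuted blocks of random size, stratified by location (two strata). The section continues: "Randomization lists will be provided to the study coordinator and another study team member not affiliated with clinical care and assessments", whose task is "to place the allocations into number opaque envelopes". Then "These envelopes will be pulled sequentially by the surgeon or study team as a patient is deemed provisionally eligible for the study". The envelope ID goes into the patient's research record, and the section says that this procedure keeps allocation concealed.

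Other sections say who handles patients before and at enrolment:

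- Section 5.4: patients "will be screened for study eligibility by the research staff".
- Section 6.1: "The subject will be approached for consent by the research staff and enrolled", after an investigator has verified eligibility.
- Section 10.1.1: "an investigator/research coordinator will approach each patient or legally authorized representative (LAR) to explain the nature of the study".

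The synopsis (1.1) adds that staff who collect and record data are masked to tube size.

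**The concern.** Concealment requires that whoever decides whether and when a patient is approached cannot know the next allocation. Here a person whose job title points to recruitment work receives the full list, and no rule keeps that person, or the other holder, away from recruitment.

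The trial gives staff a motive to act on such knowledge, even in good faith. Section 2.3.3 concedes that 14 Fr patients may have more retained hemothorax. Someone who sees that the next slot is 14 Fr might hold back a patient who looks likely to drain poorly. That lowers the 14 Fr failure rate and makes a false claim of non-inferiority easier. The intention-to-treat and per-protocol analyses in 9.4.1 cannot repair selection that happens before randomisation.

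**Working it through.** **1. Roles side by side**

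| Task | Assigned to | Section |
|---|---|---|
| Generate lists | Study statistician | 6.4 |
| Receive lists, fill envelopes | Study coordinator and one other team member | 6.4 |
| Screen | Research staff | 5.4 |
| Verify eligibility | An investigator | 6.1 |
| Seek consent, enrol | Research staff; investigator or research coordinator | 6.1; 10.1.1 |
| Pull the envelope | Surgeon or study team | 6.4 |
| Rule keeping list holders out of these tasks | None stated | – |

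**2. The qualifier.** By position, the phrase about clinical care and assessments attaches to the other team member. If it is read to cover the coordinator too, it still names only care and assessments. Seeking consent, enrolling and pulling an envelope are not plainly either of these.

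**3. The overlap.** Both list holders belong to the study team, and 6.4 lets the study team pull envelopes. Section 10.1.1 lets a research coordinator seek consent. At a single centre (4.1) this is probably the study coordinator of 6.4, but the documents do not say so.

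**4. The other safeguards.** Random block sizes and opaque envelopes stop staff guessing the next allocation; they do not stop someone who has read the list. Sequential use and recorded IDs would expose a skipped envelope, but not a patient who was never approached. Masking of data collectors concerns outcome recording. A list holder who also collects data could look up the arm from the recorded envelope ID. Section 6.4 does not say whether envelopes are sealed, who keeps them, or what happens to the list once they are filled.

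**5. Illustrative size.** The plan has no figure of its own here.

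- From section 9.2: 126 per arm, margin 8 points, failure 7% with 28 Fr and up to 15% with 14 Fr, α = 0.05 (taken as one-sided). Since 15% − 7% = 8%, these rates lie exactly on the margin, so any non-inferiority claim is false.
- Assumed: a share s of would-be 14 Fr patients is steered away, with failure risk r of 30% or 40%. They are replaced, so that each arm stays at 126, and the 28 Fr rate stays at 7%.
- Formula: 14 Fr rate after steering = (0.15 − s × r)/(1 − s). For s = 0.05 and r = 0.30: (0.15 − 0.015)/0.95 = 0.1421.
- False-claim rate: exact binomial enumeration of the Farrington-Manning score test, ignoring the interim looks.

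| Steered (s) | 14 Fr rate, r = 30% | False claim | 14 Fr rate, r = 40% | False claim |
|---|---|---|---|---|
| 0 | 15.0% | 5.0% | 15.0% | 5.0% |
| 1% | 14.85% | 5.4% | 14.75% | 5.7% |
| 2% | 14.69% | 5.8% | 14.49% | 6.4% |
| 5% | 14.21% | 7.4% | 13.68% | 9.5% |
| 10% | 13.33% | 11.2% | 12.22% | 18.0% |

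If the steered patients carry average risk (r = 15%), the 14 Fr rate stays at 15% and the false-claim rate at 5.0%.

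**The case against.** The case against has real force on several points.

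- *Roles.* A reader might infer that the study coordinator screens patients and pulls envelopes. No section says so: screening falls to research staff, pulling to the surgeon or study team, and consent to an investigator or a research coordinator, a different job title. This stands. What remains is that nothing forbids the overlap.
- *The qualifier.* It may have been meant for both people, and assessments might include assessing eligibility. The wording is ambiguous, but even the generous reading leaves consent, enrolment and envelope pulling open.
- *Existing protection.* A statistician's list, random blocks, numbered opaque envelopes, sequential use and recorded IDs are genuine safeguards. They work against guessing, not against a person who has seen the list.
- *Mechanism and direction.* Steering is hypothetical. The surgeon may be the one who pulls the envelope, and an investigator verifies eligibility. Staff who favour the small tube could also steer the other way, which would bias against non-inferiority. This stands, and it rules out any claim that the bias must favour 14 Fr.
- *Size.* The steered share and the risk of those steered come from no document, and the true rates are set on the margin, so the table is illustrative only.
- *Another route.* Under 1.2 and 10.1.1, patients with GCS below 15 (or their representatives) may be approached after insertion, within 24 hours. Their allocation is then known whoever held the list. This stands as a limit on the fix.

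**Conclusion.** The point holds as a gap in a stated procedure. Section 6.4 says who gets the list, the recipients are not kept apart from enrolment, and the claim of preserved concealment does not follow from the text. It rests on reading 6.4 with 5.4, 6.1 and 10.1.1. The link between the two coordinator titles is probable, not established, but the gap does not depend on it, because the study team as a whole may pull envelopes.

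A reader might go further and conclude that concealment was broken, or that the trial's false-positive rate is a particular figure above 5%. The documents support neither: they describe a plan, not conduct, and contain no estimate of steering. Under the stated assumptions the illustration runs from 5.4% (1% steered, 30% risk) to 18.0% (10% steered, 40% risk), against 5.0% with none. The recommendation rests on the cheapness of closing the gap, not on those figures.

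**What to change.** In section 6.4, give the list only to the other team member already named there. State that this person fills the envelopes and takes no part in screening, consent, enrolment, envelope opening or data collection. State also that the study coordinator, and anyone who seeks consent or enrols, does not see the list.

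The synopsis gives the trial's status as recruiting, so lists may already have been distributed. If so, the statistician should regenerate the unused allocations, because new wording cannot undo what has been seen.

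Cost: a sentence or two in 6.4, no extra staff, and no change to sample size or analysis. If lists are already out, add the work of new lists and envelopes. One small loss is the second person who could cross-check envelope filling; the statistician could do this instead.

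The change does not reach consent after insertion in patients with GCS below 15, which needs separate consideration.
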